6.6.1. Contraindicated medications

Subjects receiving or who have received in the past 30 days prior to enrollment these CONTRAINDICATED medications (Category D and X per Lexi-Comp interaction analysis) will be excluded from the study (Exclusion Criterion 19):

1. Pimozide (Orap®)
2. Quinidine or Quinine
3. Vitamin K Antagonists including Warfarin (Coumadin®)
4. Phenytoin (Dilantin®)
5. Rifampin (Rifadin®) and other Rifamycin derivatives (Rifapentine, Rifabutin)
6. Tofacitinib (Xeljanz® or Jakvius®)
7. Methadone
8. Sirolimus (Rapamune®), Tacrolimus (Prograf®), Everolimus (Afinitor®)
9. Rivaroxaban (Xarelto®)
10. Citalopram (Celexa®) or Escitalopram (Lexapro®)
11. Quetiapine (Seroquel®)
12. Fluoxetine (Prozac®)
13. Lomitapide (Juxtapid®)
14. Ziprasidone (Geodon®)
15. Thioridazine
16. Paliperidone (Invega®) or Iloperidone (Fanapt®)
17. Amiodarone

18. Sotalol
19. Procainamide
20. Dofetilide
21. Ibutilide
22. Dronedarone
23. Ivabrandine (Corlanor®)
24. Disopyramide
25. Erythromycin [only allowed if prescribed within the past 72 hours]
26. Clarithromycin [only allowed if prescribed within the past 72 hours]
27. Ospemifene (Osphena®)
28. Tolvaptan (Samsca®)

6.6.2. Drug Interactions with Fluconazole

The following drugs have been reported to have drug interactions with fluconazole but are not contraindications for concomitant dosing. If a potential subject is receiving one of these medications, use clinical judgment to assess potential safety impact of the agent based on its dose and expected duration of use:

1. Sulfonylureas oral hypoglycemic (Talbutamide®, Glipizide® etc)
2. Theophylline
3. Triazolam (Halcion®)
4. Amitriptyline (Elavil®) or Nortriptyline (Pamelor®)
5. Celecoxib (Celebrex®)
6. Carbamazepine (Tegretol®)
7. Cyclosporin (Sandimmune® - systemically administered)
8. Statins (Lipitor®, Zocor®, Crestor®, etc)
9. Losartan (Cozaar®)
10. Vitamin A
11. Calcium channel blockers (Norvasc®, Procardia®, etc.)
12. Short-acting benzodiazepines (Versed®, Halcion®)

-
13. Vardenafil (Levitra®) or Avanafil (Stendra®)
 14. Zolpidem (Ambien ®)
 15. Ranolazine (Ranexa®)
 16. Tizanidine (Zanaflex®)
 17. Suvorexant (Belsomra®)
 18. Solifenacin (Vesicare®)
 19. Eplerenone (Inspra®)
 20. Clopidogrel (Plavix ®)
 21. Fentanyl (Duragesic®)
 22. Buspirone (Buspar ®)
 23. Cilostazol (Pletal®)
 24. Colchicine

6.7. Rescue Procedures

Subjects who meet any of the following criteria will be removed from the treatment arm, informed of their treatment assignment, and referred to a healthcare provider for continuing of care.

1. Subsequent hospitalization for this CAP episode occurring greater than 72 hours after study randomization.
2. Worsening oxygenation: need for assisted ventilation including continuous positive airway pressure (CPAP), bilevel positive airway pressure (BIPAP), or mechanical ventilation.
3. Determined by a physician's discretion to require additional therapy not indicated in the protocol to ensure his/her health and well-being

After a subject meets one of these criteria, they will be referred back to the health care provider. All available coccidioidal serologic results will be made available to the subject. All participants will be invited to remain in study follow-up. Participants who discontinue treatment due to rescue therapy may be eligible to participate in another study for an alternative coccidioidomycosis pneumonia treatment.

7. STUDY SCHEDULE

7.1. Pre-Screening Assessment [Optional] (occurring up to 72 hours prior to enrollment)

NOTE: For situations in which performance of safety laboratory assessments in advance of screening visit allow for greater feasibility. For patients referred to study with existing standard of care safety labs, physical exam, and/or ECG within the past 72 hours and are available to the study team at the time of screening, these SOC activities can serve as the screening activities and do not require repeating. (Safety laboratory tests are required to have the same normal range values as the primary study site).

The following activities will be performed:

- Provide potential subjects with an abbreviated description of this trial and ask them to read and sign the pre-screening informed consent form. The pre-screening informed consent form will be signed prior to performing any screening procedures.
- Perform an HIV antibody test (point of care (POC) or local clinical laboratory)
- Collect approximately 10 mL of venous blood for Hepatic function panel (AST, ALT, Alkaline phosphatase and total bilirubin), BUN, Creatinine.
- Record a resting (5-minute rest period) 12-lead ECG.
- Notify the potential subject that they will receive a telephone call with the results of the safety laboratory testing (including: AST, ALT, Alkaline phosphatase and total bilirubin, BUN and creatinine) and ECG results to review and explain test results and whether they are eligible to participate in the study. Subjects without a history of prolonged QTc, whose baseline ECG shows prolonged QTc interval may be asked to return for repeat 12-lead ECG prior to determination of eligibility status. Eligible subjects will be asked to return for enrollment visit with the study team.
- The investigator will inform the subject of the results of the POC HIV -1 antibody test and provide counseling as to the meaning of the results, whether positive or negative. If the POC HIV-1 antibody test is positive and the participant does not have a prior diagnosis of HIV infection, the subject will be no longer be considered eligible for participation in the study. Counseling regarding the preliminary result and the need for a confirmatory test should be done by the site research team. A positive confirmatory test for those patients with a positive POC HIV testing will require counseling about the results and a recommendation to follow-up for care, preferably in person. Newly diagnosed HIV infections will receive additional counseling concerning the significance and possible risks to other people. Individuals with newly diagnosed HIV infections will be referred to the subjects' clinical care provider and

any other appropriate local resource. All test results, positive or negative, will be kept confidential to the extent permissible under the law. All positive results will be reported to the state's Division of Public Health as required by law. All confirmatory testing will be done following the institution's policy or the standard of care.

7.2. Screening/Enrollment/Baseline (Day 1, Visit 01)

NOTE: If referred to the study from another facility, potential subjects should be screened only if the subject can be enrolled and first dosing of study product will occur within 72 hours from discharge from the facility in where the decision to treat with antibacterials for CAP has occurred. For patients referred to study with existing standard of care safety labs, physical exam, and/or ECG within the past 72 hours and are available to the study team at the time of screening, these SOC activities can serve as the screening activities and do not require repeating. (Safety laboratory tests are required to have the same normal range values as the primary study site). The following activities will be performed:

- Provide subjects with a description of this trial and ask them to read and sign the informed consent form. The informed consent form will be signed prior to performing any study procedures, including any screening procedures.
- Collect demographic data including employment status and school/education enrollment.
- Review eligibility criteria with subjects.
- Review medical records to ensure eligibility.
- Record date of X-ray, if a chest X-ray was performed in establishing the diagnosis of this episode of CAP.
- Interview subjects and obtain medical history.
- Record medication history including the name and total daily dose of medication over the past 30 days, including vitamins, over-the-counter, and prescription drugs.
- Record vital sign measurements (sitting blood pressure, sitting heart rate, respiratory rate, oral temperature and oxygen saturation), height and weight.
- Record a resting (5-minute rest period) 12-lead ECG. (will not need to be repeated if completed as part of pre-screening assessment)
- Complete physical examination by a clinician licensed to make medical diagnoses.
- Complete FLEET CAP Score
- Complete Extra-Pulmonary Symptom Score

-
- Complete SF-12v2
 - Complete PROMIS Item Bank v2.0 - Ability to Participate in Social Roles and Activities - Short Form 4a
 - Perform a urine or serum pregnancy test on all women of childbearing potential. Test must be negative to ensure eligibility.
 - Perform a point of care (POC) HIV antibody test. (will not need to be repeated if completed as part of pre-screening assessment)
 - Collect approximately 10 mL of venous blood for Hepatic function panel (AST, ALT, Alkaline phosphatase and total bilirubin), BUN, Creatinine. (will not need to be repeated if completed as part of pre-screening assessment)
 - Collect approximately 15 mL of venous blood for Coccidioidal serologies (CF; qualitative IDCF and IDTP; EIA-IgM; EIA IgG; and quantitative IDCF)
 - In addition the subject will be allowed the option to consent for additional sample collection (urine specimen, blood specimen [20 mL], nasopharyngeal swab, and throat swab) to be banked and used in future studies
 - The investigator will inform the subject of the results of the POC HIV -1 antibody test and provide counseling as to the meaning of the results, whether positive or negative. If the POC HIV-1 antibody test is positive and the participant does not have a prior diagnosis of HIV infection, the subject will no longer be considered eligible for participation in the study and the study product should not be administered. Counseling regarding the preliminary result and the need for a confirmatory test should be done by the site research team. A positive confirmatory test for those patients with a positive POC HIV testing will require counseling about the results and a recommendation to follow-up for care. Newly diagnosed HIV infections will receive additional counseling concerning the significance and possible risks to other people. Individuals with newly diagnosed HIV infections will be referred to the subjects clinical care provider and any other appropriate local resource. All test results, positive or negative, will be kept confidential to the extent permissible under the law. All positive results will be reported to the state's Division of Public Health as required by law. All confirmatory testing will be done following the institution's policy or the standard of care.
 - The investigator must review all safety laboratory results (including: AST, ALT, Alkaline phosphatase and total bilirubin, BUN, and creatinine), ECG results for QT prolongation, pregnancy test results, POC HIV test and eligibility criteria before the subject is randomized. Subjects who do not qualify for the study based on the results of the screening procedures

should not be randomized. Subjects whose baseline ECG shows prolonged QTc interval may be asked to return for repeat 12-lead ECG prior to determination of eligibility status. Counseling regarding POC HIV testing and risk of false positives should occur by the site research team prior to the test being done.

- Enroll subjects in AdvantageEDC.
- Dispense the next available treatment assignment in sequence of study product (fluconazole or placebo) available at the site. Regardless of time the product is dispensed, observe subject taking 2 capsules (at once) in the clinic, and instruct subject to select a time of day to take their daily dose. If dosing cannot occur within 72 hours of the discharge from the facility where antibacterials for CAP were prescribed, then the subject should not be dosed and study activity must cease. Ideally, pills should be taken at the same time each day. Instruct subjects to bring their pill bottles to each visit. Review with subject that the study product should be stored at room temperature. Dispense 2 study product bottles (bottle A and B).
- Instruct subjects to notify the study center if they develop any severe reactions after study product dosing. If the site principal investigator or appropriate sub-investigator deems the reaction severe enough, further instructions will be given to the subject on the proper course of action, including a return to the clinic for immediate evaluation if appropriate.

Documentation of the subject's fulfillment of the entry criteria, for all subjects considered for the study and subsequently included or excluded, is to be completed. Documentation of screening failure details may be recorded using eligibility screening forms or a subject screen failure log. Screen failures will be entered in AdvantageEDC.

7.3. Follow-up (Days 22-180, Visits 02-07)

7.3.1. Follow-up Visit Visit 02 (Day 22):

(Window: Day 20 to Day 23):

- Interview subjects and review the medical record for interim medical history, including an assessment for new medical conditions and symptoms, hospitalizations, diagnosis of disseminated coccidioidomycosis. Note any changes since the previous clinic visit.
- Perform a urine or serum pregnancy test on all women of childbearing potential. The test must be negative to ensure continued eligibility.
- Review any concomitant medications since previous study visit. Record all concomitant medications on the appropriate data collection form.
- Review of inclusion/exclusion criteria by clinician licensed to make medical diagnoses to determine continued eligibility.

-
- Perform a targeted physical examination if indicated based on review of complete medical history and any updates obtained by interview of subjects since the Day 1 visit by a clinician licensed to make medical diagnoses.
 - Record vital sign measurements (sitting blood pressure, sitting heart rate, respiratory rate, oral temperature, oxygen saturation and weight).
 - Query subject regarding whether the subject has taken their dose for today. If the subject has not yet taken their dose for today, subject should be instructed to take the day's dose in the clinic, prior to the pill count.
 - Perform a pill count of study product (fluconazole or placebo) and interview to determine adherence. Review need to bring pill bottles for count to each visit, study product dosing and storage requirements and ability to meet requirements with subject.
 - Following pill count, collect the pill bottle A and retain until study product accountability has been completed by the study monitor.
 - Note any discrepancies between expected and actual pill count remaining in pill bottle B.
 - Review randomization number assigned at Visit 01 and dispense final bottle (bottle C) of study product. Instruct the subject to continue to take daily doses from pill bottle B and to begin taking their daily doses from the newly dispensed bottle (bottle C) once bottle B is empty.
 - If subject did not return the pill bottle A dispensed at Visit 01, instruct them to return this bottle at their next visit.
 - Complete FLEET CAP Score
 - Collect the number of days missed from school and/or work due to illness for subjects who were either enrolled in school or employed at baseline
 - Complete PROMIS Item Bank v2.0 - Ability to Participate in Social Roles and Activities - Short Form 4a
 - Complete Extra-Pulmonary Symptom Score
 - Complete SF-12v2
 - Draw venous blood samples for the following:
 - Safety laboratories (Hepatic function panel (AST, ALT, Alkaline phosphatase and total bilirubin), BUN, Creatinine) [10 mL]

-
- Coccidioidal serologies (CF; qualitative IDCF and IDTP; EIA-IgM; EIA IgG; and quantitative IDCF) [15 mL]
 - Quantitative fluconazole level [5 mL]
 - Blood to be banked for future use if consent obtained [15 mL]
 - Assess any SAEs and record on the SAE form and in AdvantageEDC.

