3.1.3. Exploratory

- To assess the effect of early empiric fluconazole therapy on the immune response to coccidioidomycosis in subjects with suspected coccidioidomycosis pneumonia.
- To assess the effect of early empiric fluconazole therapy on the development of extrapulmonary symptoms associated with coccidioidomycosis pneumonia.

-
- To assess the effects of early empiric fluconazole therapy on the occurrence of disseminated coccidioidomycosis in subjects with pneumonia in coccidioidomycosis-endemic areas.
 - To characterize the natural history of coccidioidomycosis disease by examining the clinical response and its individual components over time, in placebo recipients with coccidioidomycosis pneumonia.
 - To assess the clinical response of early empiric antifungal therapy with fluconazole at Day 22 in subjects with coccidioidomycosis pneumonia based on an alternative serologic case definition for coccidioidomycosis pneumonia.
 - To compare the clinical signs and symptoms of community-acquired pneumonia caused by coccidioidomycosis pneumonia with the clinical signs and symptoms caused by non-coccidioidomycosis pneumonia in coccidioidomycosis-endemic areas.
 - To characterize the safety of early empiric antifungal therapy with fluconazole with respect to liver function in subjects with pneumonia in coccidioidomycosis-endemic areas.
 - To assess the adherence to long term self-administration of daily fluconazole or placebo in a clinical trial setting using self-reported adherence and pill count.
 - To assess medication adherence in the active fluconazole arm by measuring fluconazole levels.

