- The proportion of subjects who received at least one dose of the intervention and who exhibit an increase in liver function tests from baseline (pre-treatment Day 1) as defined as: confirmed AST elevation of >5X ULN or greater than or equal to 225 IU/L or ALT elevation of >5X ULN or greater than or equal to 250 IU/L or total bilirubin elevation >1.5X ULN or aminotransferase elevation of >3X ULN accompanied by total bilirubin elevation >1.5X ULN.

Exploratory Outcome 8:

- The adherence to long term self-administration of daily medications will be assessed in this order of precedence:
 - First: The mean number of pills taken as assessed by pill-count on Days 22, 29 and 43.
 - Second: Subject self-reported adherence as reported on Days 22, 29 and 43.

Exploratory Outcome 9:

- The proportion of subjects with a detectable fluconazole level as assessed by blood test on Days 22 and 43 in fluconazole recipients.
 - Plasma fluconazole concentration will be determined by high-performance liquid chromatography (HPLC)

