7.3.3. Follow-up Visit 04 (Day 43)

(Window: Day 42 to Day 46)

NOTE: All assessments for this visit must be completed before the subject or study staff performing the assessments are informed of the treatment assignment and whether they met the protocol definition of acute coccidioidomycosis pneumonia

- Interview subjects and review the medical record for interim medical history, including an assessment for new medical conditions and symptoms, hospitalizations, diagnosis of disseminated coccidioidomycosis. Note any changes since the previous clinic visit.
- Perform a targeted physical examination if indicated based on review of complete medical history and any updates obtained by interview of subjects since the Day 1 visit by a clinician licensed to make medical diagnoses.
- Record vital sign measurements (sitting blood pressure, sitting heart rate, respiratory rate, oral temperature, oxygen saturation and weight).
- Perform a urine or serum pregnancy test on all women of childbearing potential.
- Review any concomitant medications since previous study visit. Record all concomitant medications on the appropriate data collection form.
- Perform a pill count of study product (fluconazole or placebo) and interview to determine adherence.

-
- Following pill count, collect the pill bottle (bottle C) and retain until study product accountability has been completed by the study monitor.
 - Complete FLEET CAP Score
 - Collect the number of days missed from school and/or work due to illness for subjects who were either enrolled in school or employed at baseline
 - Complete PROMIS Item Bank v2.0 - Ability to Participate in Social Roles and Activities - Short Form 4a
 - Complete Extra-Pulmonary Symptom Score
 - Complete SF-12v2
 - Draw venous blood samples for the following:
 - Safety laboratories (Hepatic function panel (AST, ALT, Alkaline phosphatase and total bilirubin), BUN, Creatinine) [10 mL]
 - Coccidioidal serologies (CF; qualitative IDCF and IDTP; and quantitative IDCF) [15 mL]
 - Quantitative fluconazole level [5 mL]
 - Blood to be banked for future use if consent obtained [15 mL]
 - Assess any SAEs and record on the SAE form and in AdvantageEDC.

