8.2.2.3. Fluconazole Serum Levels

Quantitative fluconazole testing will be performed at ARUP laboratories. Venous blood samples (approximately 5mL at each visit, for a total of 10 mL) will be collected on study Days 22 and 43.

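### At Day 22 the fluconazole sample may follow a supervised clinic dose, and Exploratory Outcome 9 scores it only as detectable or not, so for those subjects it is weak evidence of adherence

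*Combined protocol and SAP*

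**What the plan says.** One exploratory objective (Section 3.1.3) is "To assess medication adherence in the active fluconazole arm by measuring fluconazole levels". Exploratory Outcome 9 (Section 3.2.3) measures it as "The proportion of subjects with a detectable fluconazole level as assessed by blood test on Days 22 and 43 in fluconazole recipients". No concentration threshold is given, although the assay is quantitative. Section 8.2.2.3 adds: "Venous blood samples (approximately 5mL at each visit, for a total of 10 mL) will be collected on study Days 22 and 43".

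At the Day 22 visit (Section 7.3.1) staff ask whether that day's dose has been taken. The instruction that follows is: "If the subject has not yet taken their dose for today, subject should be instructed to take the day's dose in the clinic", and this is to happen before the pill count. The list continues with the pill count, bottle handling, the FLEET CAP score, days missed and the three questionnaires. Blood samples come after these, and the fluconazole level is among them.

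At Day 43 (Section 7.3.3, "Window: Day 42 to Day 46") a level is also drawn, but there is no instruction to dose in the clinic. Neither visit list has a step that records the time of the last dose or of the draw.

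Adherence for the primary per-protocol population comes from the pill count, or from self-report if no count is available (Section 3.2.1). Exploratory Outcome 8 uses the same two sources.

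**The concern.** The drug level is the only planned adherence measure that depends neither on the subject's account nor on returned bottles. It is therefore the natural cross-check, in the fluconazole arm, on the 80% rule applied through pill count or self-report.

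A site that works down the Day 22 list in order gives the dose first and samples later. A detectable result in a clinic-dosed subject then cannot be told apart from the effect of that single observed dose, and the proportion detectable would look reassuring even where doses had been missed. The yes/no cut-off adds to this, because it discards the concentration that the laboratory already reports.

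**Working it through.** The documents give no expected detectable proportion, detection limit, absorption time or half-life, so there is no stated figure to reproduce. The check sets the steps side by side and adds bounding arithmetic.

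**1. Order of steps.** The only order that Section 7.3.1 states is dose before pill count. The blood draw appears last in the list. Nothing requires it to follow the dose, and nothing requires a pre-dose sample. Table 12 marks fluconazole monitoring at Days 22 and 43 without any timing.

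**2. How little drug could still score as detectable.** Inputs: two capsules daily (Section 6.2), an observed two-capsule dose on Day 1 (Section 7.2), and the 80% cut (Section 3.2.1).

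- Expected by Day 22: 22 × 2 = 44 capsules.
- Adherence cut: 0.80 × 44 = 35.2, so 36 capsules.
- Observed Day 1 dose plus clinic Day 22 dose: 2 + 2 = 4 capsules, and 4/44 = 9%.

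Such a subject is far below the cut, but could be scored detectable if the draw follows the dose and drug is measurable by then.

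**3. Effect on the reported proportion (illustration, assumed inputs).** Let *a* be the share of fluconazole recipients with no measurable drug on arrival at Day 22. Let *u* be the share of those who take the clinic dose and are measurable at the draw. Then

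proportion detectable = (1 − a) + a × u.

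A pre-dose draw corresponds to u = 0.

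| a | u = 0 | u = 0.5 | u = 1 |
|---|---|---|---|
| 5% | 95% | 97.5% | 100% |
| 10% | 90% | 95% | 100% |
| 20% | 80% | 90% | 100% |
| 40% | 60% | 80% | 100% |

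With 500 subjects on fluconazole (Table 1) and a = 20%, the count is 400, 450 or 500. At u = 1 the Day 22 result is 100% whatever the value of a. The documents fix neither a nor u, so the table shows the direction and the bounds and is not an estimate.

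**4. Day 43.** If the last dose is on Day 42, a visit between Day 42 and Day 46 falls 0 to 4 days later. But Section 4 gives a course of 42 days, while Section 6.2 gives 42 days as a minimum. Three bottles of 34 capsules (Sections 6.1.2, 7.2 and 7.3.1) hold 102 capsules, which is 102/2 = 51 days of dosing. Some subjects could still be dosing at the visit, so the time since last dose cannot be inferred from the visit date. Section 2.3.1 says that elimination half-life varies inversely with creatinine clearance, so the same gap need not mean the same thing in every subject.

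**The case against.** The strongest reply is that the draw order is inferred from bullet position. That is weak evidence: in the Day 1 list (Section 7.2), HIV counselling that must precede the test appears after it. The manual of procedures, which is not supplied, may settle the order. This stands, and it is why the point is that no rule protects a pre-dose sample, and not that the dose always comes first.

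Second, staff ask every subject about that day's dose, and Section 6.5 requires records of product administered. Clinic-dosed subjects may therefore be identifiable. That helps only if the answer and the times reach the database, and no visit step says they do. Sections 11.4.4 and 11.4.4.3 defer the exploratory analyses to a separate statistical analysis plan, also not supplied. It could add a concentration analysis, but it could not recover a draw order or dose times that were never captured.

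Third, the 4-of-44 subject is extreme and would return 40 more capsules than expected, so a pill count would expose the shortfall. That is true when the bottles come back with the untaken capsules. The level adds most where they do not.

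Fourth, an earlier draw does nothing about a poor adherer who took one dose at home that morning. That is correct, and it is the reason to report concentration and dose time as well as to move the draw.

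A reader might go further and infer that the levels cannot serve the adherence objective at all, or that the primary analysis is compromised. The documents support neither. Home-dosed subjects and Day 43 samples are free of the clinic dose, and the assay returns a concentration. The level plays no part in the per-protocol rule.

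**Conclusion.** The point holds as a limited weakness in one exploratory outcome. For subjects dosed in the clinic at Day 22, a detectable level may reflect that dose alone and is weak evidence of earlier adherence. This rests on two assumptions: that the site draws after the dose, as the list order suggests, and that drug is measurable by the time of the draw. The number of subjects affected cannot be derived from the documents.

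For everyone else the clinic dose is not the problem. The detectable/not cut-off still says little about missed doses, and the Day 22 and Day 43 results are not on the same footing because the interval from last dose is neither set nor recorded in the visit text. No primary or secondary result changes. The case for acting is that better information is available from a sample and an assay already planned.

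**What to change.** - In Section 7.3.1, state that the fluconazole sample is drawn before any in-clinic dose.
- At Days 22 and 43, record the date and time of the last dose and of the draw.
- In Exploratory Outcome 9, report the measured concentration by time since last dose and by pill-count adherence (below 80% versus at least 80%), alongside the proportion detectable.
- Reconcile the statements on course length in Sections 4 and 6.2, so that the Day 43 interval can be interpreted. Which one is right is not a matter for this review.

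The cost is one reordered draw at an existing visit, two extra form fields (time of last dose, time of draw) and one extra table. No further blood, visit or assay is needed, and the dosing instruction itself is unchanged.
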